#### 7.2 Acute Coronary Syndrome

The European Society of Cardiology (ESC) and the American College of Cardiology (ACC) convened a consensus conference in 1999 in order to re-examine jointly the definition of myocardial infarction (published in the year 2000 in the European Heart Journal and Journal of the American College of Cardiology).(6) Given the considerable advances in the diagnosis and management of myocardial infarction since the original document was published, the leadership of the ESC, the ACC and the American Heart Association (AHA) convened, together with the World Heart Federation (WHF), a Global Task Force to update the 2000 consensus document.(7)

The acute coronary syndrome model espoused by the American College of Cardiology places unstable angina, non-ST-segment elevation myocardial infarction (NSTEMI) and ST-segment elevation myocardial infarction (STEMI) at increasingly severe points along a disease continuum.(6;8) At presentation, the working diagnosis of non-STE-ACS (NSTE-ACS), based on the measurement of troponins, is further classified into non-ST elevation MI, (NSTEMI) or unstable angina. The therapeutic management is guided by the final diagnosis.(9)

Registry data consistently show that NSTE-ACS is more frequent than STE-ACS.(10) The annual incidence is  $\sim$  3 per 1000 inhabitants, but varies between countries.(11) Hospital mortality is higher in patients with STEMI than among those with NSTE-ACS (7% vs. 3-5% respectively), but at six months the mortality rates are very similar in both conditions (12 and 13%, respectively).(10;12;13)

Rivaroxaban is the only novel oral anticoagulant to have received a licence for this indication in the EU.

#### 7.3 ATLAS ACS 2 TIMI 51

ATLAS ACS 2 TIMI 51 (Anti Xa Therapy to Lower cardiovascular events in addition to standard therapy in subjects with Acute Coronary Syndrome – Thrombolysis in Myocardial Infarction 51) study was published in the NEJM, in January 2012.(4)

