#### 9.7.1 To quantify the cumulative incidence (risk and rate) of major bleeding according to the TIMI classification of non-CABG Related Bleeding (Table 1) occurring in the 12 week observation period, overall and stratified by intracranial, gastrointestinal and urogenital bleeding sites.

The following relates to Section 8.2 primary objective and relates to haemorrhage within gastrointestinal and urogenital organ sites (which meets the criteria for a TIMI major non CABG related bleed) and all intracranial sites (as defined in Table 1). This time to event analysis will be performed separately for the rivaroxaban exposed cohort and the contextual cohort, as defined according to exposure at index (date antiplatelet therapy was prescribed as part of the acute management of the ACS).

<sup>1 In the event of a change in treatment resulting in a switch in treatment group, person-time contributed will be censored at the time of switching, thus analysis will not be 'intention to treat' as this is an observational study.

For each cohort, for whom acute management of ACS applies, the numerator for this analysis will comprise of adjudicated incident major bleeding events (overall and stratified by intracranial, gastrointestinal and urogenital bleeding sites) defined according to primary objective that were reported during the 12 week observation period post index date. These adjudicated events will have been reviewed by an expert panel using all available information from SCEM questionnaires, follow-up and any additional documentation. Patients for whom events were misreported will be excluded from the analysis (events will be excluded, but denominator data will still be included); patients for whom events were misclassified will be reclassified as appropriate. In addition, for each cohort, for the three organ sites specified in the primary outcome, counts of each of the individual components of the TIMI major non CABG related bleeding criteria will be summarised. Where an individual has one or more criterion for an individual organ site of interest, counts will also be summarised – in such individuals the first report will be regarded as the incident event. Since SCEM data are right censored, the cumulative incidence (risk and rate) of the primary outcomes reported during treatment within the 12 week observation period will be calculated using survival analysis methodology.

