For each individual case, relevant person-time will be estimated according to duration of observation up to event date. For each individual non-case, relevant person-time will estimated by either exit date – index date; or censor date – index date; or stop date (+ 2 days ) – index date. For each cohort separately, a semi-parametric time-dependent Cox Proportional Hazards regression model will be used to estimate the crude cumulative incidence over the 12 week observation period.

Non-parametric Kaplan-Meier plots will be presented to describe time-to event as well as smoothed estimates of the empirical hazard function to describe how the crude baseline risk of the event changes over time.

Estimates of the hazard function will also be modelled to determine whether the baseline hazard (risk) of the event increases or decreases with time. A constant hazard over time may be consistent with a background (not caused by the drug) event rate, whereas a non-constant hazard over time may be an indicator of a drug-event relationship. The null hypothesis that the hazard rate of the selected event in patients will be constant during the 12 week period following the start of treatment will be tested

<sup>1 This excludes patients prescribed rivaroxaban 2.5mg for non-ACS related indications

<sup>2 Censor date = date of loss to follow-up

<sup>3 2 days allocated to person-time to account for half-life of drug

Version 7 Date: 30/08/2017

by fitting a parametric time to event model (e.g. Weibull). Such models have a shape parameter that indicates whether the hazard is significantly increasing or decreasing over time. At least five reports of an event are deemed necessary for modelling purposes.

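### Section 9.7.1 names an ill-specified time-dependent Cox model for a crude 12-week bleeding risk and provides for no competing event; the likely overstatement is small

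*Protocol*

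**What the plan says.** The primary objective (section 8.2) is the 12-week cumulative incidence, as risk and rate, of TIMI major bleeding unrelated to CABG. It is analysed in each cohort separately. Section 9.7.1 first gives the general approach: "cumulative incidence (risk and rate) of the primary outcomes reported during treatment within the 12 week observation period will be calculated using survival analysis methodology". It then names the estimator: "a semi-parametric time-dependent Cox Proportional Hazards regression model will be used to estimate the crude cumulative incidence over the 12 week observation period". Kaplan-Meier has a descriptive role only: "Non-parametric Kaplan-Meier plots will be presented to describe time-to event".

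For patients without an event, "relevant person-time will estimated by either exit date – index date; or censor" date, or treatment stop plus 2 days. A footnote reads "Censor date = date of loss to follow-up"; exit date is not defined. For a change of treatment group, "person-time contributed will be censored at the time of switching". Death is named neither as a reason for censoring nor as a competing event. A fatal bleed is itself an outcome event (Table 1).

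The only time-varying covariate in the protocol, an exposure indicator that changes from 0 to 1, is defined later in section 9.7.1 for a sensitivity analysis on immortal time. Date and cause of death are collected on both the specialist and the GP questionnaire (sections 9.3.2 and 9.3.3).

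**The concern.** The sentence that fixes how the headline result is computed does not determine the computation. A Cox model fitted within one cohort needs a covariate before it has anything to estimate beyond the baseline hazard, and none is given. The term time-dependent then either has no referent or points to the sensitivity-analysis covariate. In the second case the primary and sensitivity analyses merge, and there is no longer one crude risk to report.

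Death is the second part. A patient who dies without a major bleed is a non-case whose person-time ends, in an analysis justified because the data are right censored. Any one-sample survival estimate built that way describes the bleeding risk as if nobody died of anything else. It is therefore equal to or higher than the cumulative incidence with death counted as a competing event. The protocol's background (section 7.2) cites mortality of 3% to 7% in hospital and 12% to 13% at six months, so deaths may well outnumber an outcome expected in 0.5%. At stake are a reproducible primary estimate and a small bias that always runs upward.

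**Working it through.** **1. The plan's own figure.** Inputs from section 9.5: p = 0.005, half-width d = 0.004, 95% confidence.

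- n = 1.96² × p(1 − p) / d² = 3.8416 × 0.004975 / 0.000016 = 1194.5, against the stated 1193.
- A finite-population correction with a population of 1,000,000 (inferred, not stated) gives 1194.5 / (1 + 1193.5/1,000,000) = 1193.1. The figure reproduces.
- At n = 1193 the standard error is √(0.004975/1193) = 0.20 points, the half-width is 1.96 × 0.204 = 0.40 points, and 1193 × 0.005 ≈ 6 bleeds are expected (about 1.2, 3.6 and 1.2 for intracranial, gastrointestinal and urogenital sites).

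**2. What the named model returns.**

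*No covariate.* The partial likelihood has no parameter. What remains is the Breslow cumulative hazard H = Σ dⱼ/nⱼ and the risk 1 − exp(−H). Kaplan-Meier gives 1 − Π(1 − dⱼ/nⱼ). For illustration, take six single events with 1193 at risk throughout:

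- Breslow: H = 6/1193 = 0.005029, risk 0.5017%.
- Kaplan-Meier: 1 − (1 − 1/1193)⁶ = 0.5019%.

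In 4,000 simulated cohorts of 1193 (0.5% bleeding, 8% death), the two never differed by more than 0.0006 points. The Cox model adds no numerical error of its own.

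*With the 0/1 exposure covariate.* The output is a coefficient β and a baseline cumulative hazard H₀. The 12-week risk is then 1 − exp{−[H₀(s) + e^β (H₀(12) − H₀(s))]}, which depends on the chosen treatment start s. There is no single crude cumulative incidence.

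**3. Size of the effect if non-bleeding deaths are censored.** Assumption: 12-week mortality D from causes other than the outcome is 2% to 10%. The documents give no 12-week figure, and this range is set around their in-hospital and six-month figures. Both hazards are taken as constant.

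- H_b = −ln(1 − 0.005) = 0.00501 and H_d = −ln(1 − D).
- Deaths censored: 1 − exp(−H_b) = 0.500%.
- Death competing (Aalen-Johansen): H_b/(H_b + H_d) × [1 − exp(−(H_b + H_d))].

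| D | H_d | Deaths censored | Death competing | Gap (points) | Relative | Share of 0.4 points | Bleeds in 1193 |
|---|---|---|---|---|---|---|---|
| 2% | 0.0202 | 0.500% | 0.495% | 0.005 | 1.0% | 1.3% | 0.06 |
| 5% | 0.0513 | 0.500% | 0.487% | 0.013 | 2.6% | 3.1% | 0.15 |
| 8% | 0.0834 | 0.500% | 0.480% | 0.020 | 4.2% | 5.1% | 0.24 |
| 10% | 0.1054 | 0.500% | 0.475% | 0.025 | 5.4% | 6.4% | 0.30 |

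Example for 10%: 0.0050125/0.1103730 × (1 − 0.995 × 0.90) = 0.045414 × 0.1045 = 0.4746%. The simulation at 8% agrees: means of 0.502% (Kaplan-Meier), 0.501% (Breslow) and 0.481% (Aalen-Johansen).

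**The case against.** The protocol nowhere says that deaths are censored. Exit date is undefined, and the handling of competing events is often left to the statistical analysis plan, which is not shown. This stands in part: censoring of deaths is an inference, and silence alone would be no finding. But the estimator is not silent. The protocol names it, and the name does not fix a calculation.

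Four stronger readings are tempting and are not supported.

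- *The Cox model is the wrong estimator, or Kaplan-Meier is the source of the primary risk.* Without covariates, Cox gives practically the Kaplan-Meier answer, and the protocol uses Kaplan-Meier for plots only. The fault is lack of specification.
- *The overstatement is large.* If half the deaths fell in the first two weeks, 2% to 10% mortality would give 0.493% to 0.466%. With 13% mortality, mostly early, the result would be 0.440%. Patients are invited after the treatment decision and must consent (sections 9.1 and 9.2.3), so deaths before consent hardly enter the cohort. Early clustering is the least plausible case. The background figures cover ACS generally and may include fatal bleeds, which count as outcome events here.
- *The reading across cohorts is distorted.* Section 9.9 expects channelling, but nothing shows different mortality after enrolment. Even 2% against 10% would shift the contrast by only 0.495 − 0.475 = 0.02 points.
- *The error carries over to all other events.* Section 9.7.4 calculates crude risks for those as a percentage of the cohort.

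**Conclusion.** The concern holds as a point of specification with a small numerical consequence. The named model either collapses to a baseline-hazard estimate or yields no single crude risk, so section 9.7.1 does not say how the primary result is obtained. On the natural reading of the person-time rules, the reported risk is also too high, by about 0.005 to 0.025 points on 0.50% under constant hazards and an assumed 12-week mortality of 2% to 10%. The upper end is about one eighth of the sampling standard error (0.025/0.20) and less than a third of one bleed in 1193 patients. The direction is certain if non-bleeding deaths are censored; the size rests on the mortality assumption. The sample size is unaffected, and no conclusion is likely to change. The case for correcting it is that the bias runs one way only and is cheap to remove.

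**What to change.** In section 9.7.1, replace the Cox sentence with text to this effect:

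- The 12-week risk in each cohort is the Aalen-Johansen cumulative incidence, with death without a primary bleed as a competing event.
- Person-time remains censored at treatment stop plus 2 days and at a switch of treatment group, so the estimate is an on-treatment risk and should be labelled as such. Treating death as competing does not turn it into the plain proportion of all patients who bleed.
- The rate is first events divided by person-time, with an exact Poisson interval.
- The time-varying Cox model is used for the immortal-time sensitivity analysis only. The Kaplan-Meier plots stay descriptive.

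The cost is a wording change and one standard routine. No new data are needed, since dates and causes of death are already collected. The reported risk becomes marginally lower than one minus Kaplan-Meier.

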#### 8.2 Objectives:

Primary objective

- to quantify the cumulative incidence (risk and rate) of major bleeding according to the TIMI classification of non-CABG Related Bleeding (Table 1) occurring in the 12 week observation period, overall and stratified by the following bleeding sites:
  - o Intracranial,
  - o Gastrointestinal
  - o Urogenital

Secondary objectives

- 1. Advancing the understanding of the patient population prescribed rivaroxaban in combination with standard oral antiplatelet therapy for ACS in the secondary care hospital setting including drug utilisation characteristics
- 2. Describing changes of health profile of patients, assessment of adherence, number of indication related episodes (ACS related events), plus any alterations of the treatment programme in respect of antiplatelet and anticoagulant therapy during the 12 week study observation period
- 3. Quantifying the risk of other major (in any other site not specified in the primary objective) or minor bleeding outcomes (in any site) reported in the 12 week observation period overall (Tables 1 and 2) and, if number of reports are sufficient, in patient subgroups of special interest in first 12 weeks of treatment under conditions of the routine secondary care hospital setting in England and Wales.

Both the primary and secondary objectives relate to the rivaroxaban cohort and the contextual comparator (reference) cohort.

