Study start is defined as the date that the first patient is recruited into the study (18th September 2015), and continue for a maximum of 36 months, or until the target sample size (1193 tbc) for both cohorts has been achieved (whichever is the soonest). The final cohort sizes, period of observation and the duration of the SCEM study will be dependent on the level of prescribing of rivaroxaban in combination with standard oral antiplatelet therapy by specialist HCPs in England and Wales. Data collected during later calendar time periods can be compared with earlier periods to identify any trends that may emerge. Slow uptake may impact on the ability to meet the study objectives; in this instance, further discussions with the regulatory authorities regarding study feasibility will be needed.

Patients will be observed from the date antiplatelet therapy was prescribed as part of the acute management of the ACS in both the rivaroxaban group and the contextual Version 7 Date: 30/08/2017

cohort for 13 weeks in order to allow for detection of outcomes associated with treatment initiation (this will allow for a delay between antiplatelet therapy administration as part of the acute treatment for the ACS, and the subsequent start of rivaroxaban to ensure 12 complete weeks of observation time for analysis). The index date for analysis for both groups will be defined dependent on the prescribing patterns observed in real life use. Since patient care is likely to be shared between secondary and primary care for most patients during the observation period, the patient's GP will be contacted at least 13 weeks after antiplatelet therapy start date to complete an abridged questionnaire to collect any information on outcomes of interest that they are aware of during the observation period to minimise under-reporting on selected outcomes. For the main statistical analysis, events will be censored at 12 weeks post index date, should they be reported after this time period. However, events of interest will be included and detailed in study reports even if they occurred after the 12 week time period. Where additional outcomes are identified that have not be reported by the initiating prescriber, these will be followed-up with the GP to ascertain further information.

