# 9.7.2 Advancing the understanding of the patient population prescribed rivaroxaban in combination with standard oral antiplatelet therapy for ACS in the secondary care hospital setting including drug utilisation characteristics

The following relates to Section 8.2 secondary objective 1.

<sup>1 e.g. when the shape parameter (p) for the Weibull model is equal to one, the hazard is estimated to be constant over time, if p is greater than one the hazard is increasing, if p is less than one the hazard is decreasing. The hazard function will be determined as non-constant if the 95% CI excludes the value one

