It is possible to explore the time taken for an event of interest using parametric time to event models (e.g. Weibull) as described previously, thus providing an additional tool for signal generation purposes. This approach will be explored for events of interest, where counts  $\geq 5$ . If undertaken, a sensitivity analysis will be performed to include in the numerator events reported within seven days of stopping, and extend the denominator by seven days.

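### Section 9.7.1 reads the shape of the hazard as evidence for or against a drug effect, but with the clock started at acute ACS management the shape cannot carry that meaning in either direction

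*Protocol*

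**What the plan says.** Section 9.7.1 of the protocol tests the null hypothesis that the hazard of an event is constant over the 12 weeks, using a parametric model such as the Weibull, provided there are at least five reports. It attaches a meaning to each outcome. On one side, "A constant hazard over time may be consistent with a background (not caused by the drug) event rate"; on the other, "a non-constant hazard over time may be an indicator of a drug-event relationship". The footnote on the Weibull shape parameter, printed by the heading of section 9.7.2, gives the cut-off: "The hazard function will be determined as non-constant if the 95% CI excludes the value one". Section 9.7.4 takes up the same model for events of interest with five or more reports, "thus providing an additional tool for signal generation purposes".

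Section 9.7.1 defines the index date of the primary analysis, for both cohorts, as the "date antiplatelet therapy was prescribed as part of the acute management of the ACS". Section 9.1 is less settled: "The index date for analysis for both groups will be defined dependent on the prescribing patterns observed in real life use". The time-to-event analysis is run separately in each cohort, and section 8.2 states: "Both the primary and secondary objectives relate to the rivaroxaban cohort and the contextual comparator (reference) cohort". No rule says how the two cohorts' shapes are to be read against each other. A time-varying exposure covariate is planned, but only as a sensitivity analysis for immortal time.

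**The concern.** The stated reading needs a background hazard that is flat from index to week 12. Here time on the clock is, under the section 9.7.1 definition, time since acute management of a coronary event. A hazard that falls as patients stabilise would be labelled non-constant and read as a possible drug signal, even if the contextual cohort fell in the same way. A second route to the same error is the start of rivaroxaban after the clock has begun. Section 9.7.1 concedes that the unexposed stretch is of unknown length, and it can bend the observed hazard upwards.

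The opposite reading fails for a different reason. The shape describes how the hazard changes, not how high it is. A drug that raised bleeding evenly throughout treatment would, on a flat background, give a shape of 1, which the protocol associates with an event not caused by the drug. At stake is whether a safety study requested by the CHMP may raise a signal from the disease course, or take comfort from a flat hazard at a raised level.

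**Working it through.** **Inputs from the protocol.** Section 9.5: 12-week risk 0.5% (intracranial 0.1%, gastrointestinal 0.3%, urogenital 0.1%), precision ±0.4%, 1193 patients per cohort. Section 9.7.1 and its footnote: at least five events; non-constant if the 95% CI of the shape excludes 1.

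**The plan's own figure.** n = 1.96² × 0.005 × 0.995 / 0.004² = 1194.5, against the stated 1193 (1193.0 with a finite-population correction for 1,000,000). The sample size is reproduced. The protocol states no figure for the operating characteristics of the shape test.

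**Events available.** 1193 × 0.005 = 6.0 expected primary events per cohort. The binomial chance of at least five is 71% overall, 29% for gastrointestinal bleeds alone, and 0.8% for intracranial or urogenital bleeds alone.

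**A steady excess.** The Weibull hazard is h(t) = λ·p·t^(p−1). Multiplying it by a constant c gives c·λ·p·t^(p−1), so p is unchanged whatever the size of c. On a flat background p stays at 1. In simulation (1193 patients, Wald interval on log p, at least five events) a constant hazard was flagged in 5.6%, 5.7% and 5.2% of analysable cohorts at risks of 0.5%, 1% and 2%. That is the nominal error rate at every level of risk. No assumption about early bleeding enters this step.

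**A front-loaded background with no drug effect.** The protocol gives no bleeding time course, so the share of bleeds in weeks 1 and 2 is assumed; a flat hazard gives 2/12 = 17%. Events are uniform within weeks 1–2 and within weeks 3–12, with six expected.

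| Share of bleeds in weeks 1–2 | Flagged, of analysable cohorts | Flagged, of all studies |
|---|---|---|
| 17% (flat) | about 5–6% | – |
| 40% | 12% | 8% |
| 50% | 23% | 16% |
| 60% | 38% | 27% |

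The result depends on the assumed form. With a Weibull background of shape 0.7, 0.5 or 0.4, which puts (2/12)^p = 29%, 41% or 49% of the 12-week events in weeks 1–2, the flagged shares of analysable cohorts at 0.5% risk are 12%, 40% and 62%.

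**Late start of rivaroxaban.** If no event can be counted in the first 14 days (assumed) and the hazard is flat afterwards, about 20% of analysable cohorts are flagged at six expected events, with no drug effect.

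**Non-rejection.** With six events the standard error of log p is about 1/√6 = 0.41, so an estimate anywhere from exp(−1.96 × 0.41) = 0.45 to exp(1.96 × 0.41) = 2.23 does not reject. Failure to reject is weak evidence of a constant hazard.

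**Reading against the contextual cohort.** If both cohorts share the front-loading above, a test of the shape ratio flags about 1 to 4% of studies in which it can be fitted, and about 5 to 6% under a flat hazard. With six events in each cohort, the standard error of the log ratio is √(1/6 + 1/6) = 0.58, so the ratio must fall outside about 0.32 to 3.1. At equal risks, both cohorts reach five events in about 0.71² = 50% of studies.

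**The case against.** The wording is hedged. Both sentences say that the hazard may point one way or the other, and the one firm rule declares a hazard non-constant, not an event drug-related. Section 9.7.4 asks for medical judgement, section 9.7.5 puts events in context by temporality and pre-existing disease, and section 9.9 says that features of the indication will be considered when signals are investigated. All of this stands. It softens the consequence but does not make the stated reading correct.

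A reader might infer that the plan as a whole would miss a steady excess. The protocol does not support that: section 9.7.1 estimates 12-week risk and rate in both cohorts, and section 9.7.4 adds incidence densities. Only the shape test is blind to level.

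A reader might also infer that the signal analyses have no comparator. That holds for the other, non-bleeding events. Section 9.7.4 covers other major and minor bleeding in both cohorts, and section 9.7.1 produces the smoothed hazards for each.

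The most tempting stronger reading uses the mortality figures in section 7.2: 7% and 3–5% in hospital, while "at six months the mortality rates are very similar in both conditions (12 and 13%, respectively". These suggest a steeply falling background, but they do not carry over. Patients enter only after the treatment decision and with signed consent (sections 9.1 and 9.2.3), so those who die before consent are not in the data. The figures concern death, not bleeding, and would need an assumed length of hospital stay.

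Finally, the primary outcome is non-CABG bleeding at intracranial, gastrointestinal and urogenital sites, so bleeding at vascular access sites is outside it, and section 9.1 leaves the index date open. Early concentration of these bleeds is therefore possible but not established.

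**Conclusion.** The point holds as a fault in how the protocol interprets the shape test. With the clock at acute ACS management, a shape away from 1 does not separate a drug effect from time since the ACS. A shape of 1 does not point to background, because a proportional excess of any size on a flat background gives the same value. The second half follows from the algebra alone. The size of the first half rests on an assumption: with 40 to 60% of bleeds in weeks 1 and 2 and six expected events, about 12 to 38% of analysable cohorts would be flagged with no drug effect, against about 5 to 6% under a flat hazard.

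The fault is confined to signal interpretation. It leaves the primary estimates of risk and rate untouched, and the documents do not support saying that the plan would declare a drug effect automatically.

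**What to change.** Delete the section 9.7.1 sentence that links a constant hazard to an event not caused by the drug.

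For bleeding outcomes analysed in both cohorts, treat time-dependence as a possible drug signal only when the rivaroxaban shape departs from the contextual shape. Report the ratio of shapes with its CI beside both smoothed hazards. Handle time before the first rivaroxaban prescription with the time-varying exposure already planned in section 9.7.1; otherwise the late start can make the two shapes differ without a drug effect.

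State that a steady excess is judged from the two cohorts' incidence risks and rates set side by side, since the shape ratio cannot show it either. For events analysed in the rivaroxaban cohort only, report the shape as descriptive; this keeps the scope of the exploratory objectives in section 8.2.

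The cost is a change of wording and one extra comparison per bleeding outcome, on data already collected in both cohorts. The downside is a wide interval for the ratio, which can be fitted in only about half of studies at six expected events per cohort, so fewer signals will be declared.
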